8.3. Adverse Events (AEs), Serious Adverse Events (SAEs), and Other Safety Reporting

8.3.1. Definitions

8.3.1.1. Definition of Adverse Event

An AE is any untoward medical occurrence in a participant administered a pharmaceutical product and that does not necessarily have a causal relationship with this treatment. An AE can therefore be any unfavorable and unintended sign (including an abnormal laboratory finding), symptom, or disease temporally associated with the use of an study intervention, whether or not considered related to the study intervention.

8.3.1.2. Definition of Treatment-Emergent Adverse Event

A TEAE is any condition that was not present prior to treatment with the study intervention but appeared following treatment, was present at treatment initiation but worsened during treatment, or was present at treatment initiation but resolved and then reappeared while the individual was on treatment (regardless of the intensity of the AE when the treatment was initiated).

8.3.1.3. Definition of Serious Adverse Event

A SAE or reaction is any untoward medical occurrence that, at any dose has any of the following consequences:

- Results in death
- Is life-threatening
- Requires in-patient hospitalization or prolongation of existing hospitalization
- Results in persistent or significant disability/incapacity
- Is a congenital anomaly/birth defect
- Medically significant

Note: The term “life-threatening” in the definition of “serious” refers to an event in which the participant was at risk of death at the time of the event; it does not refer to an event that hypothetically might have caused death if it were more severe.

Medical and scientific judgment should be exercised in deciding whether expedited reporting is appropriate in other situations, such as important medical events that may not be immediately life-threatening or result in death or hospitalization but may jeopardize the participant or may require intervention to prevent one of the other outcomes listed in the definition above. These should also usually be considered serious.

Important medical events that may not result in death, be life-threatening, or require hospitalization may be considered serious when, based upon appropriate medical judgment, they may jeopardize the participant or participant and may require medical or surgical intervention to prevent one of the outcomes listed in this definition. Examples of such medical events include allergic bronchospasm requiring intensive treatment in an emergency room or at home, blood dyscrasias or convulsions that do not result in inpatient hospitalization, or the development of drug dependency or drug abuse.

Hospitalizations for elective or previously scheduled surgery for pre-existing conditions, which have not worsened after initiation of treatment, will not be classed as SAEs. Previously scheduled hospitalizations must be documented in the participant’s source documents before the participant signed the ICF. A kidney biopsy performed as part of the study will not be considered an SAE. Any complication experienced during a kidney biopsy procedure resulting in hospitalization or a prolongation of the hospitalization requires SAE reporting.

8.3.1.4. Definition of an Adverse Event of Special Interest (AESI)

An AESI is an AE of scientific and medical interest specific to understanding of the study intervention and may require close monitoring and collection of additional information by the Investigator. An AESI may be serious or nonserious.

The rapid reporting of AESIs allows ongoing surveillance of these events in order to characterize and understand them in association with the use of this study intervention.

The following AESIs will be particularly monitored in this trial:

- Hypersensitivity reaction, including anaphylaxis
- Severe viral infection/reactivation (CTCAE Grade 3 or higher)
- Opportunistic infection as listed in [Appendix 2](#) (all cases)
- Malignancy (except non-melanoma skin cancer)

8.3.2. Classification of an Adverse Event

8.3.2.1. Relationship to Study Intervention

The Investigator is required to provide an assessment of the relationship of AEs and SAEs to the study intervention. An event will be considered “not related” to use of study intervention if any of the following are met:

- An unreasonable temporal relationship between administration of the study intervention and the onset of the event (eg, the event occurred either before, or too long after, administration of the study intervention for it to be considered study intervention related).
- A causal relationship between the study intervention and the event is biologically implausible (eg, death as a passenger in an automobile accident).
- A clearly more likely alternative explanation for the event is present (eg, typical adverse reaction to a concomitant drug and/or typical disease-related event).

Individual AE/SAE reports will be considered “related” to use of the study intervention if the “not related” criteria are not met.

“Related” implies that the event is considered to be “associated with the use of the drug” meaning that there is “a reasonable possibility” that the event may have been caused by the study intervention (ie, there are facts, evidence, or arguments to suggest possible causation).

8.3.2.2. Adverse Event Severity

The guidelines outlined in CTCAE v5.0 will be used for assessing the severity or intensity of the event. The general guidelines for assessing the AE grade are provided in [Table 11](#).

Table 11 CTCAE v.5.0 General Guidelines

Grade	Description
Grade 1	Mild; asymptomatic or mild symptoms; clinical or diagnostic observations only; intervention not indicated.
Grade 2	Moderate; minimal, local, or noninvasive intervention indicated; limiting age-appropriate instrumental ADL ^a .
Grade 3	Severe or medically significant but not immediately life-threatening; hospitalization or prolongation of hospitalization indicated; disabling; limiting self-care ADL ^b .
Grade 4	Life-threatening consequences; urgent intervention indicated.
Grade 5	Death related to AE.

Table 11 CTCAE v.5.0 General Guidelines

Grade	Description
	ADL = activities of daily living; AE = adverse event; CTCAE = Common Terminology for Adverse Events. The CTCAE v5.0 is dated to 27 NOV 2017.
^a	Instrumental ADL refers to preparing meals, shopping for groceries or clothes, using the telephone, managing money, etc.
^b	Self-care ADL refers to bathing, dressing, and undressing, feeding self, using the toilet, taking medications, and not bedridden.

8.3.2.3. Expectedness

Horizon Therapeutics Ireland DAC will assess the expectedness of each SAE in relation to the study intervention. Please refer to Investigator's Brochure for more details.

8.3.3. Time Period and Frequency for Event Assessment and Follow-Up

The occurrence of an AE or SAE may come to the attention of trial personnel during trial visits and interviews of a trial participant presenting for medical care, or upon review by a trial monitor.

All AEs, including local and systemic reactions, will be captured on the appropriate eCRF. Information to be collected includes event description, date of onset, clinician's assessment of severity, relationship to study intervention (assessed only by those with the training and authority to make a diagnosis), and date of resolution/stabilization of the event. All AEs occurring while on trial must be documented appropriately regardless of relationship.

Trial site personnel will note the occurrence and nature of each participant's medical condition(s) present prior to the informed consent signature in the appropriate section of the source document and eCRF. During the trial, site personnel will note any change in the condition(s) and the occurrence and nature of any AE.

Any medical condition that is present prior to informed consent signature will be considered as part of medical history and not reported as an AE. However, if the trial participant's condition deteriorates after the consent signature, it will be recorded as an AE.

Should a participant experience an AE at any time after the informed consent signature until the end of participation in the trial, the event will be recorded as an AE in the source document and eCRF. Any SAE related to the trial participation (eg, screening procedure) will be recorded in the source document and eCRF from the time consent is given to participate in the trial until the end of participation in the trial.

The Investigator is responsible for appropriate medical care of participants during the trial. The Investigator also remains responsible for following through with an appropriate health care option for all AEs that are ongoing at the end of the trial. The participant should be followed until the event is resolved or stable. If an AE is ongoing at the end of trial, the follow-up duration is left to the discretion of the Investigator. Follow-up frequency will be performed at the discretion of the Investigator.

Whenever possible, clinically significant abnormal laboratory results are to be reported using the diagnostic that resulted in the clinically significant abnormal laboratory results and not the actual abnormal test.

8.3.4. Adverse Event Reporting

Investigators are responsible for monitoring the safety of participants who are participating in this trial and for alerting the Sponsor to any event that seems unusual, even if this event may be considered an unanticipated benefit to the participant.

8.3.5. Serious Adverse Event Reporting

Horizon Therapeutics Ireland DAC will be the pharmacovigilance unit responsible for the overall pharmacovigilance process for this trial. All SAEs, related to the experimental treatment or not, occurring during the course of the trial must be reported by entering the information into the eCRF on an SAE form to the pharmacovigilance unit (see below contact information) within 24 hours of the knowledge of the occurrence (this refers to any AE that meets one or more of the aforementioned seriousness criteria). The SAE reporting period ends at the end of the Follow-Up Period or if the participant begins an alternative therapy.

Reporting should be done by sending the completed SAE form to the following e-mail address (faxing may also be done as a second option in case e-mailing is not possible).

Safety Contact Information: Horizon Therapeutics

E-mail: [contact]

US [contact]

The pharmacovigilance unit will inform the Medical Monitor, the Sponsor, and the Contract Research Organization (CRO) within 1 business day of awareness of a new SAE. The pharmacovigilance unit will process and evaluate all SAEs as soon as the reports are received. For each SAE received, the pharmacovigilance unit, in consultation with the Sponsor if needed, will make a determination as to whether the criteria for expedited reporting to relevant regulatory authorities have been met.

The expedited reporting of relevant safety information to concerned regulatory agencies and ethic committees will be performed in accordance with local laws and regulations and will be defined in the Safety Management Plan.

The trial Sponsor will be responsible for notifying the Food and Drug Administration (FDA) of any unexpected fatal or life-threatening suspected adverse reactions as soon as possible, but in no case later than 7 calendar days after the Sponsor's initial receipt of the information. In addition, the Sponsor must notify the FDA and all participating Investigators in an Investigational New Drug (IND) safety report of potential serious risks, from clinical trials or any other source, as soon as possible, but in no case later than 15 calendar days after the Sponsor determines that the information qualifies for reporting.

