[REDACTED] Under exceptional circumstances such as delayed laboratory results, drug washout, or the impact of COVID-19, the Screening Period may be increased by 2 weeks, upon approval by the Medical Monitor. In general, re-screening of participants may occur only in consultation with and approval by the Medical Monitor. The trial will be conducted on an outpatient basis. For all administrations, study intervention will be administered by site staff in the clinic and the participant will be observed for at least 60 minutes after the first three doses as well as at [REDACTED]

[REDACTED] Participants who prematurely stop dosing prior to Week 52 will be followed for regularly scheduled visits through Week 52 unless participants withdraw consent of trial participation (See Section 7.1.3) or are lost to follow-up (See Section 7.2). Participants should be followed to assess AE/SAEs for at least 12 weeks after the last study intervention administration, approximately 4, 8, and 12 weeks after the last study intervention dose, unless the participant withdraws consent. Participants who prematurely stop dosing after Week 52 but remain in the study will complete the End-of-Treatment (EOT) Visit and the SFU Period, unless the participant withdraws consent. Participants will not automatically be removed from the trial if any administration of study intervention is missed.

Rescue therapy for worsening LN may be administered at the discretion of Investigators as clinically indicated. Rescue therapy includes the initiation of any new treatment for lupus or lupus nephritis or an increase from baseline in the standard-of-care background therapy (MMF/MPA, or corticosteroids). For any rescue medications, study intervention may be continued after discussion with and approval by the Horizon Medical Monitor. However, if the participant receives a prohibited medication as a rescue, study intervention will be discontinued (See Section 6.7.2). Participants who receive rescue therapy will be considered treatment failures for subsequent endpoint analyses (such as CRR).

The primary assessment of the efficacy endpoints will be performed at [REDACTED]. The

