4.4. End-of-Study Definition

A participant is considered to have completed the trial if he or she was followed through the last protocol-specified visit (ie, Week 112), regardless of the number of doses of study intervention that were received as shown in the SoA (See Section 1.3).

The end of study date is defined as the date when the last participant across all sites is assessed (ie, last subject last visit), including any additional parts in the study (eg, long-term follow-up, additional antibody testing), as applicable.

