6.7.2. Prohibited Medications

Receipt of any of the following treatments leads to immediate discontinuation of study intervention:

- IV, intramuscular, or SC immunoglobulins, except anti-SARS-CoV-2 therapeutic antibodies
- Cyclophosphamide or alkylating agents (eg, chlorambucil)
- Calcineurin inhibitors (eg, cyclosporin, voclosporin, tacrolimus), mechanistic target of rapamycin inhibitors, retinoids, thalidomide, lenalidomide, or Janus kinase inhibitors.
- Transfusion with blood, packed red blood cells, platelets or treatment with plasmapheresis, plasma exchange, or Therakos® photopheresis.
- Live vaccines (the Sponsor recommends that Investigators ensure all participants are current with recommended vaccinations per local treatment standards prior to entry into the study).
- Cytokine or cytokine receptor antagonists, including but not limited to interleukin (IL)-1, IL-6, IL 17, IL-12/23, IL-23, IFN, integrin, or TNF α antagonists (except for IFN α kinoid, for which receipt at any time is exclusionary).
- Belimumab, abatacept, or eculizumab
- Other biologics used for immunosuppression or immunomodulation (eg, IFN therapy, IL-2)

- Investigational drugs
- IPP-201101 (LupuzorTM)
- B cell-depleting therapies (eg, rituximab, ocrelizumab, ofatumumab, inebilizumab, telitacicept) other than atacicept or obinutuzumab
- Receipt of systemic glucocorticoids (ie, PO, rectal, IV or IM) for more than a total of 2 weeks for any concurrent illness, including asthma, inflammatory bowel disease, or drug-induced SLE
- Atacicept
- BCG vaccination
- Obinutuzumab

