6.7.3. Restricted Medications

As daxdilimab is an investigative immunomodulatory agent, non-protocol permitted changes to immune modifiers or immunosuppressants during the study are not allowed. If a participant receives one of the following after Randomization, the Investigator must notify the Sponsor/Designee Medical Monitor immediately. The Designee Medical Monitor will determine with the Sponsor if the participant may continue to receive study intervention; however, the participant would be considered a non-responder for efficacy assessments such as CRR.

- Azathioprine
- Methotrexate
- Leflunomide
- Mizoribine
- Cholestyramine
- Increase in corticosteroids (except methylprednisolone pulses) above the protocol allowed doses or duration
- Corticosteroids with a long biologic half-life (ie, dexamethasone, betamethasone)
- MMF/MPA dose above or below protocol required dose or duration

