7.1.2. Discontinuation from the Trial

Reasons for discontinuation from the trial include the following:

- The participant is lost to follow-up.
- The Sponsor or regulatory authorities, for any reason, stop the trial. In this case, all participants will be discontinued from the trial. The Investigator will immediately, on discontinuance of the trial by the Sponsor, in its entirety or at a clinical trial site, inform both the participants and the research ethics board of the discontinuance, provide them with the reasons for the discontinuance and advise them in writing of any potential risks to the health of participants or other persons.

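### Protocol 8.3.5 ends SAE reporting when an undefined alternative therapy begins, although 4.1, 7.1.1 and 8.3.3 keep such participants in follow-up

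*Protocol*

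**What the plan says.** Protocol 8.3.5 sets the site's duty first: "All SAEs, related to the experimental treatment or not, occurring during the course of the trial must be reported", and this must happen "within 24 hours of the knowledge of the occurrence". It then sets the end of that duty: "The SAE reporting period ends at the end of the Follow-Up Period or if the participant begins an alternative therapy".

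Other sections say what happens to a participant who starts another therapy:

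- **Prohibited medication (6.7.2):** "Receipt of any of the following treatments leads to immediate discontinuation of study intervention". Section 7.1.1 lists it as a reason to stop study intervention and then sets out continued follow-up.
- **Restricted medication (6.7.3):** "The Designee Medical Monitor will determine with the Sponsor if the participant may continue to receive study intervention".
- **Rescue therapy (4.1, 6.7.6):** this includes any new lupus or lupus nephritis treatment. Dosing may continue with Medical Monitor approval, unless the rescue drug is a prohibited one.

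On follow-up, 4.1 says: "Participants should be followed to assess AE/SAEs for at least 12 weeks after the last study intervention administration". The exception given is withdrawal of consent. Sections 4.1 and 7.1.1 also keep participants who stop dosing before Week 52 on scheduled visits through Week 52, unless they withdraw consent or are lost to follow-up. Section 8.3.3 records adverse events from consent to the end of participation. Tables 3 and 4 of the Schedule of Activities mark AE and SAE collection as continuous. SAP 4.9.1 counts treatment-emergent events from first dose, with no cut-off when another therapy starts.

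**The concern.** The end of SAE reporting depends on an event that nobody has defined. Read broadly, alternative therapy could cover any rescue, restricted or prohibited drug. Read narrowly, it might cover only a replacement for study drug. Two sites could apply it differently and both claim compliance.

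The timing makes this matter. Under 7.1.1, lupus worsening that needs prohibited immunosuppression is itself a reason to stop study drug. New therapy can therefore begin just as the post-dose safety follow-up starts, when the participant has recently been exposed to both study drug and a new immunosuppressant. At that point the clause could release the site from the 24-hour duty. The sponsor's 7-day clock for unexpected fatal or life-threatening suspected reactions runs from its own receipt of the information, so a late site report would also start that clock late.

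**Working it through.** The plan states no figure to reproduce. The check has two parts.

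**1. Does starting another therapy end participation?** If it did, the clause would be harmless.

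- After restricted medication or non-prohibited rescue, dosing itself may continue (4.1, 6.7.3, 6.7.6), so the participant is plainly still in the trial.
- After prohibited medication, only study intervention stops (6.7.2). Section 7.1.1 then requires visits through Week 52 if the stop is before Week 52, or the End-of-Treatment Visit and Safety Follow-Up Period if it is after.
- Completion of the trial under 4.4 holds "regardless of the number of doses of study intervention that were received".

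So starting another therapy does not by itself end participation. The clause would close SAE reporting while visits, AE/SAE assessment and AE recording continue.

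**2. How much follow-up could fall after the cut-off?** Let s be the week the other therapy starts and L the week of the last dose. Both are assumptions, since the documents give no switching times or rates. For a stop before Week 52, two requirements in 4.1 and 7.1.1 apply together: visits through Week 52, and AE/SAE assessment to at least L + 12. The later end governs:

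weeks remaining = max(52 − s, L + 12 − s).

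The partly redacted synopsis text on early stopping also uses a longer-of-two rule. For a stop after Week 52, weeks remaining = L + 12 − s.

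| Last dose L | Therapy start s | Calculation | Weeks remaining (up to) |
|---|---|---|---|
| 12 | 12 | max(40, 12) | 40 |
| 24 | 24 | max(28, 12) | 28 |
| 36 | 36 | max(16, 12) | 16 |
| 40 | 40 | max(12, 12) | 12 |
| 40 | 44 | max(8, 8) | 8 |
| 40 | 48 | max(4, 4) | 4 |
| after 52 | L, L + 4, L + 8 | L + 12 − s | 12, 8, 4 |

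For any L of 40 or more, L + 12 is at least 52, so the result is 12, 8 or 4 weeks for a therapy start 0, 4 or 8 weeks after the last dose. The last three results are indexed by the last dose, not by the week therapy starts. Therapy starting at Week 40 after a last dose at Week 36 leaves max(12, 8) = 12 weeks, not 8.

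These are maxima. Footnotes to Tables 3 and 4 make the 4-, 8- and 12-week contacts depend on the agreement of participants who choose to stop study intervention. The figures also cover only participants who stop study drug. One who is rescued and keeps dosing stays on the schedule to Week 112, if rescue counts as an alternative therapy at all.

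**The case against.** The strongest reply is that 8.3.5 does not contradict itself. The first sentence gives scope and deadline and the second says when the period ends, so the second can be read as limiting the first. That is a fair reading. A reader might infer a flat self-contradiction, but the text does not force one: within the section, the two sentences merely fit poorly. The reply does not remove the conflict with 4.1, 7.1.1 and 8.3.3, which set no such limit for a participant who starts another therapy.

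A reader might also argue that new therapy is absent from the exit reasons in 7.1.2. That list carries no weight here. It opens with "Reasons for discontinuation from the trial include the following" and is not exhaustive: it omits withdrawal of consent (7.1.3) and pregnancy (8.3.6).

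The second reply is that other safeguards exist. AE and SAE collection is continuous in the Schedule of Activities, and 8.3.3 requires eCRF recording to the end of participation. Under 8.3.5, entry on an eCRF SAE form is itself part of the reporting route. Investigators must alert the sponsor to unusual events (8.3.4), 8.3.1.4 refers to rapid reporting of events of special interest, and the safety board reviews data at regular intervals. The sponsor's own duties to regulators are not ended by the clause, and the Safety Management Plan, which is not available here, may say more. All of this stands and reduces the consequence. None of the provisions in the documents restores the site's 24-hour duty once the clause applies.

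**Conclusion.** The point holds as an undefined end-of-reporting trigger that is inconsistent with required follow-up. Under the assumed timings, up to 40, 28 or 16 weeks of follow-up could fall after the cut-off when study drug is stopped and other therapy started at Week 12, 24 or 36. For a last dose at Week 40 or later, the figure is up to 12, 8 or 4 weeks.

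The consequence is a risk of late or missing 24-hour SAE reports. A reader might go further and infer that SAEs will be lost, or that the SAE tables will be biased between arms. The documents do not support either. Recording under 8.3.3 continues, and no switching rates are given, so unequal reporting by arm is only a possibility and no number of affected SAEs can be stated. The primary endpoint and its analysis are unaffected. The issue is modest in consequence but clear in the text, and worth correcting.

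**What to change.** Delete from 8.3.5 the second limb of the sentence, the one triggered by an alternative therapy, so that SAE reporting runs to the end of the participant's follow-up. If the sponsor wants to keep some limit, define the term against 6.7.2, 6.7.3 and 6.7.6 and reconcile it with 4.1, 7.1.1 and 8.3.3.

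The cost is one clause of protocol text and possibly a few more SAE reports from participants already being followed. No visits or data collection are added, and nothing about treatment changes.
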